12.0 Potential Benefits to Subjects and Others

12.1 Potential Benefits to Subjects

Sleep quality may improve (total sleep time, less frequent awakenings) over the course of the study.

12.2 Potential Benefits to Others

The results of this study may guide future treatment of insomnia in patients with opioid and alcohol dependency.

13.0 Sharing Results with Subjects

Not applicable. We will not be sharing results with participants or others.

14.0 Subject Stipend (Compensation) and/or Travel Reimbursements

Patients who are research participants will receive a \$10 gift card for each day in the study. Upon completion of the entire medication period, they will get a bonus of a \$50 gift card. The total amount they will receive for completing the entirety of the study will be \$150 in gift cards.

Although the institutional standard now is to provide payment via Greenphire clincard, the population for this study are patients in a residential treatment center for substance use disorder. Compensation for participation in the study is given in the form of Target gift cards as alcohol or tobacco cannot be purchased at Target and Greenphire clincards could be used at vendors that sell alcohol and tobacco. As such, the study team has received an exception from the controller's office to continue using gift cards (approved 08/08/2020).

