3.3 Early Withdrawal of Subjects

3.3.1 Criteria for removal from study

Subjects are free to withdraw at any time without any influence impacting their ongoing treatment. If a patient experiences side effects, these will be documented and reported to the FDA, as required.

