7.2 Study Procedures

When a medication is studied for a new indication, or in a new population, it is common (in clinical neuropsychopharmacology) to conduct the first study in an open trial. We plan to study two groups of patients in an open 7-day trial of 20 mg suvorexant HS, following a two-day baseline during which patients will be taking a previously prescribed sleep medication (i.e. trazodone, mirtazapine, or melatonin) before switching to suvorexant. The study design includes a combination of assessments, and the collection of biological samples. Participants will be enrolled in the study for a total of 10 days (9 nights). Table 1 references the daytime questionnaires and procedures, and Table 2 represents the night questionnaires and procedures. Night is considered to be the time after the patient takes the medication. In our study, the night falls after the day.

Table 1. Daytime questionnaires and procedures.

Study Day	0	1	2	3	4	5	6	7	8	9
Consent and										
Screening (Form										
90 AI/DI, MINI	X									
Screen/MINI 7.0.2,										
HAM-D)										
EMA		X	X	X	X	X	Χ	X	X	Χ
Modified ISI	Χ									Χ
Modified PSQI	Χ									
DNA Collection*	Χ									
Cortisol Collection		X	X					X	X	
Abuse Liability			X						X	
Battery – Morning			Δ						Λ	

Table 2. Night questionnaires and procedures.

Study Night	0	1	2	3	4	5	6	7	8
Suvorexant			1	2	3	4	5	6	7
Baseline**	X	X							
Suvorexant Administration			X	X	X	X	X	X	X
Actigraphy/Logs	Χ	X	X	X	X	X	X	X	X
Abuse Liability Battery - Night		X						X	
Observer Rated Questionnaire		X						X	

*Optional saliva for patients with opioid use disorder only

**Current medicine regime including antidepressants/melatonin

Abbreviations: EMA, ecological momentary assessment; ISI, Insomnia Severity Index; PSQI, Pittsburgh Sleep Quality Index.

7.2.1 Consent and Screening: Study Day 0

After signing the informed consent document, the Caron based study coordinator will complete a comprehensive screening assessment with each participant to further evaluate their eligibility in the study. The comprehensive screening assessment includes questionnaires to evaluate psychiatric comorbidities, sleep quality, depression and previous drug/alcohol use. The screening assessment questionnaires will be administered to the patients by the Caron based study coordinator on paper/ electronic tablet using the REDCap software. The screening questionnaires will include:

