7.3 Duration of Participation

Participants will be enrolled in the study for a total of 9 days.

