19.7 Stopping Rules

In the event of an adverse reaction, the participant will consult with the nursing and doctoral staff at Caron to determine if they should continue with study. If deemed appropriate, participants will be removed from the study. If this event occurs, or the patient refuses to continue with the study, they will consult their doctors, and the medication will be properly destroyed, as described in section 7.4.6.4.

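### One third of the payment depends on finishing the suvorexant course, and a patient who stops the drug has no described way to stay in the assessments

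*Combined protocol and SAP*

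**What the plan says.** Section 14.0 sets out three elements of payment: a $10 "gift card for each day in the study"; then "Upon completion of the entire medication period, they will get a bonus of a" $50 gift card; and "The total amount they will receive for completing the entirety of the study will be" $150. It gives no proration of the bonus and no exception for stopping on medical advice or after an adverse reaction.

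Section 3.3.1 says: "Subjects are free to withdraw at any time without any influence impacting their ongoing treatment". It does not mention payment.

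Under section 19.7, after an adverse reaction "the participant will consult with the nursing and doctoral staff at Caron to determine if they should continue with study", and then: "If deemed appropriate, participants will be removed from the study". Patients who are removed, or who decline to go on, see their doctors and their study medication is destroyed. Section 7.4.6.4 treats non-completers in the same way. Neither section mentions a patient who stops suvorexant but continues with actigraphy, EMA, cortisol or the ISI. Section 3.3.2 names early discharge from the treatment program as the primary expected reason for withdrawal and plans no follow-up of those patients.

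On ascertainment, section 19.2 has nursing staff ask about adverse events at every nightly administration, on all 9 nights.

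**The concern.** The bonus rewards exposure, not data. A resident who tolerates suvorexant poorly and is deciding whether to go on has $50 riding on the answer. Section 11.0 lists impaired next-day alertness and central nervous system depression among the known reactions and advises caution in patients with a history of alcohol or drug abuse, which describes everyone enrolled. An incentive to keep taking the drug is hard to justify when the same money could reward finishing the measurements.

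The second issue is the absence of an off-drug route. If a patient who stops also leaves, the end-of-study measurements go too. The paired t-tests in section 8.3 need a post-switch value. The mixed models there rely on data being missing at random, an assumption that is weaker when a patient leaves because of the drug's effects. With 10 opioid and 15 alcohol data sets expected (section 8.1), a few such losses would be noticeable.

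The two issues are linked but distinct. The bonus bears on the decision to stop; the missing route determines what is lost afterwards.

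**Working it through.** **1. Reproduce the stated total.** Inputs from section 14.0: $10 per day, $50 bonus, $150 total. Section 7.2 and its tables run from Day 0 to Day 9, which is 10 days; section 7.3 says "Participants will be enrolled in the study for a total of 9 days".

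- 10 days: 10 x $10 + $50 = $150, which matches.
- 9 days: 9 x $10 + $50 = $140, which does not match.

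The payment was evidently built on 10 days, and sections 7.2 and 7.3 need reconciling.

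**2. Bonus share.** 50/150 = 33.3% (50/140 = 35.7% on the 9-day count).

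**3. What a patient who stops loses.** Suvorexant dose k is given on Night k + 1 (section 7.2, Table 2). Assume that Day 0 is paid, that a removed patient leaves the morning after dose k (Day k + 2), and that pay ends that day. Paid days are then Days 0 to k + 2, so pay if removed = $10 x (k + 3).

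| Last dose k | Removed on | Paid | Short of $150 | Bonus part | Later daily pay |
|---|---|---|---|---|---|
| 1 | Day 3 | $40 | $110 | $50 | $60 |
| 2 | Day 4 | $50 | $100 | $50 | $50 |
| 3 | Day 5 | $60 | $90 | $50 | $40 |
| 4 | Day 6 | $70 | $80 | $50 | $30 |
| 5 | Day 7 | $80 | $70 | $50 | $20 |
| 6 | Day 8 | $90 | $60 | $50 | $10 |

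If a patient who stops were allowed to stay to Day 9, daily pay would come to 10 x $10 = $100 and the loss would be the $50 bonus alone. A patient who reports a reaction and completes all 7 doses loses $0.

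**4. What data go with removal.** Suvorexant starts on Night 2. The abuse-liability battery is scheduled for Night 1 with Day 2, and for Night 7 with Day 8. The first pair falls on the baseline medication, so the second is the only on-drug assessment. Post-switch cortisol is collected on Days 7 and 8, and the second ISI on Day 9.

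- Removed by Day 6 (k = 1 to 4): none of these is obtained.
- Removed on Day 7 (k = 5): no on-drug battery, no ISI, and at most part of the Day 7 cortisol.
- Removed on Day 8 (k = 6): the Night 7 battery is obtained; the ISI is not.

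**5. How many patients could be affected.** Section 8.1: 36 enrolled and 10 + 15 = 25 evaluable expected, so 36 - 25 = 11 (30.6%) are not. Section 8.1 does not say why. Given section 3.3.2, 11 serves as a ceiling on the expected number who stop because of the drug, not as an estimate.

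**6. Cost of paying patients who stop but stay.** Bonus only: 11 x $50 = $550. Bonus plus the largest amount of later daily pay: 11 x ($50 + $60) = 11 x $110 = $1,210. If all 36 patients completed, payments would be 36 x $150 = $5,400.

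**The case against.** A reader might infer that patients are being paid not to report reactions. The documents do not support that. No payment depends on reporting; section 19.7 leads first to a consultation, and removal follows only if judged appropriate. Nurses ask every night, and an observer-rated form is completed on Nights 1 and 7 (section 7.4.4). What remains is indirect: a patient may expect that reporting could end in removal. Its size cannot be derived from the plan.

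A reader might also treat the whole shortfall as a penalty, for example $90 for removal after the third dose. Of that, $40 is daily pay for days not yet served; only $50 is bonus. Nor does a patient who stops lose all reason to finish assessments, because the daily $10 is not tied to capsules and is two thirds of the total. The obstacle is that no off-drug route is described, and moving the bonus alone would recover no data.

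Three further objections have force. Early discharge, not intolerance, is the main expected cause of withdrawal, and no bonus wording would bring those patients back. Section 3.3.1 promises only that withdrawal will not affect treatment, so the bonus does not contradict it. The consent form (section 5.2.1) is a separate document that may contain payment terms for early withdrawal; it was not available for this review.

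Finally, patients who stop are sent to their doctors about sleep problems, so later sleep treatment may affect a Day 9 ISI taken off drug. That is fair, and is a reason to record the treatment and analyze those data separately. It is not a reason to leave the data uncollected.

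None of this alters the central point: as section 14.0 reads, stopping early costs $50 whatever the reason.

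**Conclusion.** The point holds as a cheap improvement. Stopping suvorexant early forfeits $50 of $150 (33%), with no exception for an adverse reaction. A patient who is also removed falls short of the full amount by $60 to $110, depending on when. The plan describes no way to stay in assessments off drug, so removal by Day 6 means no on-drug abuse-liability data, no second cortisol series and no Day 9 ISI.

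This rests on three readings: that the medication period in section 14.0 means the seven suvorexant nights, that Day 0 is a paid day, and that no other document changes the payment terms. It does not establish that reactions will be under-reported, that tolerability will look better than it is, or that the 11 expected non-evaluable patients would be lost through intolerance.

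**What to change.** **Section 14.0.** Pay the same $50 for completing the Day 9 assessments, and state that stopping suvorexant does not forfeit it. Say whether Day 0 is paid, and reconcile the day count between sections 7.2 and 7.3.

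**Section 19.7, with matching wording in 7.4.6.4.** Without changing who stops or when, distinguish stopping suvorexant from leaving the study. A resident who stops and agrees keeps the already scheduled assessments (actigraphy, EMA, cortisol, Day 9 ISI) and the daily payment. Flag these data as off study drug and record any later sleep medication.

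**Section 8.3.** Show on-drug analyses separately from analyses that include off-drug data. The on-drug abuse-liability measures cannot be recovered for someone no longer taking the drug, so report how many patients lack them and why.

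**Cost.** Protocol and consent wording, and at most about $1,210 in payments if all 11 expected non-evaluable patients had stopped the drug after one dose and stayed to Day 9. No new procedure or staff is needed. The scientific drawback is that off-drug data may reflect later sleep treatment, which the flag and the separate analysis make visible.

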15.0 Economic Burden to Subjects

15.1 Costs

Not applicable. Participants will not be responsible for any costs related to participation in the research.

15.2 Compensation for research-related injury

Not applicable. There are no plans for HMC/PSU to provide financial compensation or free medical treatment for any research-related injury.

16.0 Resources Available

16.1 Facilities and locations

Recruitment and study procedures will be performed at the Caron Foundation, a treatment facility in Wernersville, PA.

16.2 Feasibility of recruiting the required number of subjects

Based on our previous studies at the same treatment center, we were able to recruit 80 patients with opiate dependence within 19 months, resulting in an average of 4 patients per month. We had similar results for our alcohol study.

We will be recruiting from all units at Caron.

OUD: During a recent census, there were 31 patients on the Men's Primary Care Unit, 9 patients on the Women's Primary Care Unit, 3 on the Young Adult Female Unit, 13 on the Young Adult Men's Unit, 3 on the Grand View Manner Unit, and 13 on the Health Care Professionals Unit that had a primary diagnosis of OUD (not including Heroin). Ten (10) patients had a diagnosis of OUD only (9 Male, 1 Female); the remaining patients had a history of at least one other co-morbid SUD (e.g., cannabis, alcohol, cocaine) (47 Male, 14 Female). The men ranged in age from 18-69; the women from 18-59. Duration of Opioid use ranged from several months to 30+ years. Throughout April-June 2017, the Caron Treatment Center admitted (in those selected units) 71 patients with a diagnosis of OUD (approximately 23 patients/month).

AUD: During the most recent census, there were 63 patients on the Men's Primary Care Unit, 33 patients on the Women's Primary Care Unit, 6 on the Young Adult Female Unit, 24 on the Young Adult Men's Unit, 19 on the Grand View Manner Unit, and 11 on the Health Care Professionals Unit that had a primary diagnosis of AUD. A total of 74 patients had a diagnosis of AUD only (46 Male, 28 Female); the

remaining patients had a history of at least one other co-morbid SUD (e.g., cannabis, opiates, cocaine). The men ranged in age from 19-68; the women from 21-61. Duration of alcohol use ranged from several months to 30+ years. Throughout April-June 2016, the Caron Treatment Center admitted (in those selected units) 156 patients with a diagnosis of AUD (approximately 52 patients/month).

Not all patients will qualify or consent to be in the study. Our goal is to finish recruitment within a 1-year time period.

16.3 PI Time devoted to conducting the research

The PI will be able to devote 50% of time to conducting and completing the research, considering outside responsibilities.

16.4 Availability of medical or psychological resources

Medical and/or psychological resources will be primarily available at the Caron Foundation through their counselors and medical staff. However, the PI, [name] is a fully trained and licensed psychologist, will also be available for consultation with participants should any participant request one; and, will be on-call 24/7 if there are any complaints, questions, or concerns about the research, in regards to the study medication.

16.5 Process for informing Study Team

The research team will be given specific duties to conduct the research study. The study coordinators will be provided with training to conduct the screening process (obtain informed consent, and to oversee patient self-reports on the M.I.N.I 7.0.2, HAM-D, Form 90AI or DI, PSQI and ISI), and instruct participants on how to use the actigraphs, cortisol tubes and smart phones that are used to collect the EMA data. Staff members and nurses at Caron will be instructed on medication distribution and abuse liability procedures.

17.0 Other Approvals

17.1 Other Approvals from External Entities

The Caron Foundation has granted approval to use their facility to conduct research.

17.2 Internal PSU Committee Approvals

Check all that apply:

Anatomic Pathology – Hershey only – Research involves the collection of tissues or use of pathologic specimens. Upload a copy of HRP-902 - Human Tissue For Research Form on the "Supporting Documents" page in CATS IRB. This form is available in the CATS IRB Library.

Animal Care and Use – All campuses – Human research involves animals and humans or the use of human tissues in animals

Biosafety – All campuses – Research involves biohazardous materials (human biological specimens in a PSU research lab, biological toxins, carcinogens, infectious agents, recombinant viruses or DNA or gene therapy).

Clinical Laboratories – Hershey only – Collection, processing and/or storage of extra tubes of body fluid specimens for research purposes by the Clinical Laboratories; and/or use of body fluids that had been collected for clinical purposes, but are no longer needed for clinical use. Upload a copy of HRP-901

- Human Body Fluids for Research Form on the "Supporting Documents" page in CATS IRB. This form is available in the CATS IRB Library.

Clinical Research Center (CRC) Advisory Committee– All campuses – Research involves the use of CRC services in any way.

Conflict of Interest Review – All campuses – Research has one or more of study team members indicated as having a financial interest.

Radiation Safety – Hershey only – Research involves research-related radiation procedures. All research involving radiation procedures (standard of care and/or research-related) must upload a copy of HRP-903 - Radiation Review Form on the "Supporting Documents" page in CATS IRB. This form is available in the CATS IRB Library.

□ IND/IDE Audit – All campuses – Research in which the PSU researcher holds the IND or IDE or intends to hold the IND or IDE.

Scientific Review – Hershey only – All investigator-written research studies requiring review by the convened IRB must provide documentation of scientific review with the IRB submission. The scientific review requirement may be fulfilled by one of the following: (1) external peer-review process; (2) department/institute scientific review committee; or (3) scientific review by the Clinical Research Center Advisory committee. NOTE: Review by the Penn State Hershey Cancer Institute Scientific Review Committee is required if the study involves cancer prevention studies or cancer patients, records and/or tissues. For more information about this requirement see the IRB website at: http://www.pennstatehershey.org/web/irb/home/resources/investigator

18.0 Multi-Site Research

18.1 Communication Plans Not applicable.

19.0 Adverse Event Reporting

19.1 Adverse Event Definitions

For drug studies, inc	orporate the following definitions into the below responses, as written:
Adverse event	Any untoward medical occurrence associated with the use of the drug in
	humans, whether or not considered drug related
Adverse reaction	Any adverse event caused by a drug
Suspected adverse	Any adverse event for which there is a reasonable possibility that the drug
reaction	caused the adverse event. Suspected adverse reaction implies a lesser degree
	of certainty about causality than "adverse reaction".
	 Reasonable possibility. For the purpose of IND safety reporting,
	"reasonable possibility" means there is evidence to suggest a causal
	relationship between the drug and the adverse event.
Serious adverse	Serious adverse event or Serious suspected adverse reaction: An adverse event
event or Serious	or suspected adverse reaction that in the view of either the investigator or
suspected adverse	sponsor, it results in any of the following outcomes: Death, a life-threatening
reaction	adverse event, inpatient hospitalization or prolongation of existing
	hospitalization, a persistent or significant incapacity or substantial disruption
	of the ability to conduct normal life functions, or a congenital anomaly/birth
	defect. Important medical events that may not result in death, be life-

	threatening, or require hospitalization may be considered serious when, based upon appropriate medical judgment, they may jeopardize the patient or subject and may require medical or surgical intervention to prevent one of the outcomes listed in this definition.
Life-threatening	An adverse event or suspected adverse reaction is considered "life-
adverse event or	threatening" if, in the view of either the Investigator (i.e., the study site
life-threatening	principal investigator) or Sponsor, its occurrence places the patient or research
suspected adverse	subject at immediate risk of death. It does not include an adverse event or
reaction	suspected adverse reaction that had it occurred in a more severe form, might
	have caused death.
Unexpected	An adverse event or suspected adverse reaction is considered "unexpected" if
adverse event or	it is not listed in the investigator brochure, general investigational plan, clinical
Unexpected	protocol, or elsewhere in the current IND application; or is not listed at the
suspected adverse	specificity or severity that has been previously observed and/or specified.
reaction.	

For device studies, incorporate the following definitions into the below responses, as written:				
Unanticipated	Any serious adverse effect on health or safety or any life-threatening problem			
adverse device	or death caused by, or associated with, a device, if that effect, problem, or			
effect	death was not previously identified in nature, severity, or degree of incidence			
	in the investigational plan or IDE application (including a supplementary plan			
	or application), or any other unanticipated serious problem associated with a			
	device that relates to the rights, safety, or welfare of subjects.			

19.2 Recording of Adverse Events

Subjects will be routinely questioned about adverse events from nursing staff at Caron during each nightly administration (all 9 nights of the study). Information will also be collected through the modified abuse liability assessment where patients will be given the Drug Effect questionnaire, administered 30 minutes after drug administration, and the next morning, to be used to evaluate how strong a drug effect was felt on a 5-item response scale, ranging from No Drug Effect to Very Strong Effect. This assessment will be administered in the evening of Study Night 1, as well as the morning of Study Day 2. Nursing staff will also complete an observer-rated questionnaire 30 minutes after drug administration on Study Night 1 and 7.

All adverse events should be reported immediately and will be addressed by the physician and other staff at Caron. The staff at Caron will then complete a Suvorexant Adverse Reaction Documentation form. All forms will be sent to and reviewed by the PI on our study team, [name]. In the event of a serious or life threatening adverse reaction, Caron medical staff will be immediately informed and address the situation. [name] will be contacted within 12 hours. Subjects are also encouraged to call the PI (with the assistance of the staff at Caron), [name] at [name] (cell) if they have questions, complaints or concerns about the research or believe they may have been harmed by being in the research study.

All adverse events (serious or non-serious) and abnormal test findings observed or reported to study team believed to be associated with the study drug(s) or device(s) will be followed until the event (or its sequela) or the abnormal test finding resolves or stabilizes at a level acceptable to the investigator.

An abnormal test finding will be classified as an adverse event if one or more of the following criteria are met:

• The test finding is accompanied by clinical symptoms

- The test finding necessitates additional diagnostic evaluation(s) or medical/surgical intervention; including significant additional concomitant drug treatment or other therapy
 NOTE: Simply repeating a test finding, in the absence of any of the other listed criteria, does not constitute an adverse event.
- The test finding leads to a change in study drug dosing or discontinuation of subject participation in the clinical research study
- The test finding is considered an adverse event by the investigator.

